## PROTOCOL SUMMARY OF CHANGES

**RPCI # I 145208 / NCI 7870**

**Amendment:** RPCI #31 / CTEP #32 Protocol Dated: 5/29/19

**Study Title:** Phase I / II Study of High Dose Interleukin 2, Aldesleukin, in Combination with the Histone Deacetylase Inhibitor Entinostat in Patients with Metastatic Renal Cell Carcinoma

Section	Page	Rationale	Previous Text	New Text
Title Page	1	Updated for submission	Amendment # 30 10/11/18 (CTEP version 10/9/18 Amendment # 31)	Amendment # 31 05/29/19 (CTEP version 10/9/18 Amendment # 32)
Footer	All	Updated for Submission	10/11/18	5/29/19
4.3	17	Updated to add in termination language once primary endpoint is met.	
Duration of Follow Up
 
Follow up safety evaluations will occur 30 days (+/- 4 days) after last dose of study drug or until resolution of any drug related toxicity (telephone contact is acceptable). Follow up will include review of concomitant medications and adverse events.
 
Patients (both Phase I and Phase II) will be followed up after completion of therapy every three months for survival assessment (telephone contact is acceptable).
	
Duration of Follow Up
 
Follow up safety evaluations will occur 30 days (+/- 4 days) after last dose of study drug or until resolution of any drug related toxicity (telephone contact is acceptable). Follow up will include review of concomitant medications and adverse events.
 
Patients (both Phase I and Phase II) will be followed up after completion of therapy every three months for survival assessment (telephone contact is acceptable) or until completion of primary endpoint/ termination of study.

ICF Changes	ICF Addendum-separate document	ICF Addendum	10/11/18	5/29/19

**Title: Phase I/II Study of High Dose Interleukin 2, Aldesleukin, in Combination with the Histone Deacetylase Inhibitor Entinostat in Patients with Metastatic Renal Cell Carcinoma**

## 1. OBJECTIVES

### 1.1 Phase I Primary Objectives

1.1.1 To evaluate the safety and tolerability of high dose interleukin 2 (aldesleukin) in combination with entinostat in patients with metastatic renal cell carcinoma (RCC).

### 1.2 Phase II Primary Objectives

1.2.1 To monitor toxicity and estimate the efficacy of high dose aldesleukin combined with entinostat in patients with metastatic RCC.

### 1.3 Phase II Secondary Objectives

1.3.1 To compare the time-to-tumor progression, progression-free survival and overall survival of patients with metastatic RCC treated with high dose aldesleukin combined with entinostat to the historical data of patients treated with high dose aldesleukin alone.

1.3.2 To assess the toxicity of high dose aldesleukin combined with entinostat.

1.3.3 To evaluate entinostat pharmacodynamics (PD) in blood and tumor samples.

1.3.4 To measure the association between baseline laboratory parameters (e.g. CD4+, CD8+, CD4+/Foxp3), tumor blood metabolism, and a variety of response variables (e.g. toxicity, response and survival).

1.3.5 To explore the relationship between entinostat exposure with PD endpoints (e.g. toxicity and histone acetylation in peripheral blood mononuclear cells or PBMNCs and changes in T cell subset population).

1.3.6 To evaluate the modulation of tumor metabolism by FDG PET/CT scan.

## 2. BACKGROUND

### 2.1 Renal cell carcinoma

More than 51,000 new cases of kidney cancer and approximately 13,000 cancer specific deaths in the United States have been predicted for 2007. One third of patients have metastatic disease at the time of diagnosis. Two randomized studies in metastatic RCC patients have shown survival benefit of nephrectomy and cytokine therapy over cytokine therapy alone. Many patients undergo nephrectomy as a component of their standard care. The prognosis for recurrent or metastatic renal cell carcinoma is poor, as median survival is 10-13 months and 5-year survival is less than 5%. These figures underscore the need for effective systemic therapy in this disease.

In 1992, high-dose bolus aldesleukin was approved by the FDA for the treatment of patients with metastatic renal cell cancer based on data presented on 255 patients entered into 7 phase II clinical trials. HD bolus aldesleukin is superior in terms of response rate and response quality to regimens involving either intermediate or low dose aldesleukin or subcutaneous interferon alpha (IFN $\alpha$ ).

### 2.2 Interleukin 2 (Aldesleukin)

The Cytokine Working Group performed a phase III trial in which patients were randomized to

NCI Protocol #: 7870

receive either outpatient aldesleukin (5 MIU/m^2 subcutaneously every 8 hours x 3 doses on day 1 then daily 5 days/week for 4 weeks) and IFN $\alpha$  (5 MIU/m^2 subcutaneously thrice weekly for 4 weeks) every 6 weeks or standard high dose inpatient aldesleukin (600,000 IU/kg/dose every 8 hours intravenously, days 1-5 and 15-19 [max 28 doses]) every 12 weeks. The response rate for high-dose aldesleukin was 23% (22/95) versus 10% (9/91) for aldesleukin / IFN $\alpha$  (p=0.018). Eight patients achieved a complete response on high dose aldesleukin versus only 3 on low dose aldesleukin / IFN $\alpha$ . The median response durations were 24 months for high dose aldesleukin and 15 months for aldesleukin / IFN $\alpha$  (p=0.18). Median overall survivals were 17 and 13 months (p=0.21), favoring high dose aldesleukin. Ten patients on high dose aldesleukin were progression free at 3 years versus 3 on aldesleukin / IFN $\alpha$  (p=0.08). Durable CRs favored HD aldesleukin (7 vs. 0). Median progression free survival was 3 months for each treatment arm. Another three-arm randomized study compared response rates and overall survival for patients with metastatic RCC receiving high-dose or one of two low-dose aldesleukin regimens. Major tumor regressions, as well as complete responses, were seen with all regimens tested but high dose aldesleukin was more clinically active, although this did not produce an overall survival benefit. Taken together these data suggests that high dose aldesleukin should remain the preferred therapy for appropriately selected patients with access to such therapy before or after the use of the recently FDA approved receptor tyrosine kinase inhibitors sorafenib and sunitinib. However, given the toxicity and limited efficacy of high dose aldesleukin therapy, additional efforts should be directed to increase the efficacy of immunotherapy.

### 2.3 Histone deacetylase inhibitors

Histone deacetylases (HDACs) are critically important in the regulation of gene expression and in the field of target-specific anticancer drug. Inhibitors of HDAC present an exciting, novel approach to the treatment of solid tumors, many of which are refractory to current therapies. Several chemical groups of HDAC inhibitors have been identified: 1) *short-chain fatty acids* – butyrates 2) *hydroxamic acids* – trichostatin A (TSA), suberoylanilide hydroxamic acid (SAHA or vorinostat), oxamflatin and LBH-589; 3) *cyclic tetrapeptides containing a 2-amino-8-oxo-9,10-epoxy-decanoyl (AOE) moiety* – trapoxin A; 4) *cyclic peptides not containing the AOE moiety* – depsipeptide and apicidin and 5) *benzamides* – entinostat.

The HDACs exert their targeted action during post-translational acetylation of core nucleosomal histones, which affects chromatin structure, thereby regulating gene expression. DNA that is wrapped around condensed, non-acetylated histones is transcriptionally inactive, whereas acetylation of N-terminal histone lysine residues exposes DNA to important transcription factors that promote transcriptional activity. The dynamic equilibrium between histone acetylation and deacetylation is regulated by histone acetyltransferases (HATs) and HDACs. The action of HDACs on nucleosomal histones leads to tight coiling of chromatin and silencing of expression of various genes, including those implicated in the regulation of cell survival, proliferation, differentiation, and apoptosis. The effects of HDACs are not limited to histone deacetylation. HDACs also act as members of a protein complex to recruit transcription factors to the promoter region of genes, including those of tumor suppressors, and they affect the acetylation status of specific cell cycle regulatory proteins.

## 2.4 Entinostat

The synthetic benzamide, entinostat has demonstrated induction of chromatin hyper-acetylation and antitumor activity by inhibition of HDAC enzyme activity. Entinostat has also demonstrated inhibition of tumor cell growth in nude mice that was comparable or superior to conventional cytotoxic agents. The results from the Phase I testing of entinostat have been recently published. Patients with advanced solid tumors or lymphoma were treated with entinostat orally initially on a once daily x 28 every 6 weeks (daily) and later on once every-14-days (q14-day) schedules. The starting dose was 2 mg/m^2 and the dose was escalated in three- to six-patient cohorts based on toxicity assessments. With the daily schedule, the MTD was exceeded at the first dose level. PK analysis suggested the half-life of entinostat in humans was 39 to 80 hours, substantially longer than predicted by preclinical studies. With the q14-day schedule, 28 patients were treated. The MTD was 10 mg/m^2 and dose-limiting toxicities were nausea, vomiting, anorexia, and fatigue. Exposure to entinostat was dose dependent, suggesting linear PK. Increased histone H3 acetylation in peripheral-blood mononuclear-cells was apparent at all dose levels by immunofluorescence analysis. Ten of 29 patients remained on treatment for > or = 3 months. The entinostat oral formulation on the daily schedule was intolerable at a dose and schedule explored. The q14-day schedule is reasonably well tolerated. Histone deacetylase inhibition was observed in peripheral-blood mononuclear-cells. Based on PK data from the q14-day schedule, more frequent dosing schedules such as weekly x 4, repeated every 6 weeks have been tested. In a Phase I study (Berlex 306121) the MTD for entinostat dosed on D1, D8, D15 of 4 weeks cycle was established at 4mg/m^2 dose level. Most common toxicities hypophosphatemia (grade 3 in 48% of patients) bone marrow suppression, gastrointestinal events such as nausea and vomiting (grade 1 + 2 frequent) fatigue, asthenia (grade 1 +2 frequent, hypoalbuminemia, hypoproteinemia.

[figure not shown]
## 2.5 Rationale for the combination of entinostat and high dose aldesleukin

HDAC inhibitors induce cell-cycle arrest, differentiation or apoptosis *in vitro*, and have potent anti-tumor activities *in vivo*. We have previously showed HDAC inhibitor entinostat has a significant antitumor activity in a renal cell carcinoma model. HDAC inhibitors have been also shown to have immunodulatory properties including activation of major histocompatibility complex (MHC) class I and II proteins, and co-stimulatory molecules CD40, CD80 and CD86. The results from the clinical trials with HDAC inhibitors in cutaneous T cell lymphoma and large cell lymphoma patients suggest that the antitumor activity these agents may be in part due to the modulation of the immune response.

In our lab, we have recently tested the effectiveness of combination therapy of aldesleukin with the HDAC inhibitor entinostat in a murine renal cell carcinoma (RENCA) model. RENCA-luciferase expressing cells were implanted in the left kidney of BALB/C mice. Animals were randomly divided in four groups and treated with either vehicle, 150,000 IU aldesleukin twice daily by i.p injections (twice weekly for two weeks), 5 mg/kg entinostat daily by oral gavage (5 days/week for two weeks), or combination. Treatment was started 3 days following tumor cell injection. Weekly luciferase images and tumor weight after 3 weeks treatment showed significant tumor inhibition (>80%) in the as compared to aldesleukin (no significant inhibition) or entinostat (~40% inhibition) (see Panel A and B). Spontaneous lung metastases were also

**NCI Protocol #: 7870**

inhibited in the combination treatment (>90 % inhibition) as compared to single treatment. Kaplan-Meier analyses showed statistically significant increase in survival in the combination group as compared with control and single agents (Panel C). The percentage of CD4+ 25+ and Fox-p3+ T cells was increased or reduced, respectively, in lymph nodes from tumor bearing animals treated with the combination of entinostat and aldesleukin as compared to control and single agents (Panel D). Splenocytes from mice treated with combination treatment showed greater lysis than splenocytes from mice treated with single agents (Panel E). These results suggest that combination of aldesleukin and entinostat has a synergistic antitumor effect in vivo in an immunocompetent murine model of renal cell carcinoma. The antitumor effect was associated with decreased number of regulatory T cells and increased antitumor cytotoxicity by splenocytes. Lower dose aldesleukin (15,000 IU) also induced a greater antitumor effect as compared to single agents (Panel F). However, microscopic examination revealed the presence of tumor in all the samples suggesting a dose-dependent effect of aldesleukin in this combination (Panel G). Blood samples collected after two hours from entinostat administration revealed a median plasma concentration of  $20.6 \pm 5.01$  ng/ml.

In summary, these results suggest that combination of aldesleukin and entinostat has a synergistic antitumor effect in vivo in an immunocompetent murine model of renal cell carcinoma. The antitumor effect was associated with decreased number of regulatory T cells and increased antitumor cytotoxicity by splenocytes. A dose dependent effect for aldesleukin but not for entinostat was observed. In conclusion, these data provide the rationale for clinical testing of the combination of high dose aldesleukin and HDAC inhibitors in the treatment of renal cell carcinoma patients. The immunomodulatory activity of entinostat and its direct antitumor effect may increase the response rate to high dose aldesleukin, further delay disease progression and increase progression-free survival in patients with metastatic RCC.

## 2.6 Rationale for entinostat dose and schedule selection

Entinostat has been evaluated in vitro, in non-clinical in vivo studies, and in phase 1 studies in patients with various solid tumors and hematological malignancies at doses between 2 and 12 mg/m^2 and at dosing frequencies ranging from once daily to every 2 weeks. Increased histone acetylation was observed at the lowest dose evaluated with the effect persisting at least 48 hours post-dose. Pharmacokinetic studies of entinostat have indicated a long half-life of entinostat, **Patients may have received up to two prior therapies including VEGF, mTOR and PD-1/PDL1 inhibitors** ranging from 40 hours to 120 hours, with concentrations detectable 168 hours post-dose at doses of 6 mg/m^2 to 12 mg/m^2, consistent with this long half-life.

The MTD for single agent in non-hematologic indications has been established as 4mg/m^2 weekly x 3 and one week rest, or 10 mg/m^2 every second week continuously. In combination with 13-*cis*-retinoic acid the MTD is also 4 mg/m^2 weekly x 3 with one week of rest. For hematologic indications the MTD is 6 mg/m^2 weekly x 3 and one week rest.

Approximately 40% variability in clearance of entinostat was noted. When clearance was adjusted for body surface area, the inter-patient variability was similar. A linear regression analysis on factors that may contribute to this variability, such as ideal body weight, lean body mass, body weight, and body mass index, were not significant covariates. As a result of this analysis, fixed dosing is considered to be as accurate as dosing based on body surface area. Therefore, based on the clinical experience with entinostat, a dose of 3 and 5 mg given every 2 weeks has been selected as the regimen for this study. Combination studies with flat every 2 weeks dose of entinostat are currently conducted in breast and lung cancer. Antitumor response has been reported in patients with melanoma treated with 3 mg every 2 weeks dose.

Our preclinical data suggest that the immunomodulatory effect of entinostat is observed 7-14 days after administration. The every 2 week schedule will allow the pharmacodynamic assessment of entinostat as single agent and eventually prime the immune response to high dose aldesleukin administration.

## 3. PATIENT SELECTION

### 3.1 Eligibility Criteria

- 3.1.1 Patients must have pathological diagnosis of renal cell carcinoma that is metastatic or surgically unresectable. The histology must be clear cell carcinoma or predominant clear cell carcinoma.
- 3.1.2 Patients may have received up to two prior therapies including VEGF, mTOR and PD-1/PDL1 inhibitors. Prior palliative radiation to metastatic lesion(s) is permitted, provided there is at least one measurable and/or evaluable lesion(s) that has not been irradiated.
- 3.1.3 Patients must have measurable or evaluable disease.

- 3.1.4 Age  $\geq$  18 years.
- 3.1.5 ECOG performance status 0 (see Appendix B).
- 3.1.6 Life expectancy of greater than 6 months.
- 3.1.7 Patients must have normal organ and marrow function as defined below:
- Hemoglobin  $\geq$ 12 g/dL
  - Leukocytes  $\geq$ 3,000/mm^3
  - Absolute neutrophil count  $\geq$ 1,500/mm^3
  - Platelets  $\geq$ 100,000/mm^3
  - Total bilirubin  $\leq$ 1.5 x laboratory upper limit of normal
  - AST(SGOT)/ALT(SGPT)  $\leq$ 2.5 x laboratory upper limit of normal
  - Creatinine  $\leq$ 1.5 x laboratory upper limit of normal or Calculated Creatinine clearance of  $\geq$ 50ml/min (please use institutional formula)
  - LDH WNL
  - Corrected calcium  $\leq$ 10 mg/dL
  - PT/INR  $\leq$ 1.5
  - Urine protein  $<$ 1+; if  $\geq$ 1+, 24 hour urine protein should be obtained and should be  $<$ 1000 mg
- 3.1.8 Pulmonary: FEV1  $\geq$ 2.0 liters or  $\geq$ 75% of predicted for height and age. (PFTs are required for patients over 50 or with significant pulmonary or smoking history).
- 3.1.9 Cardiac: No evidence of congestive heart failure, symptoms of coronary artery disease, myocardial infarction less than 6 months prior to entry, serious cardiac arrhythmias, or unstable angina. Patients who are over 40 or have had previous myocardial infarction greater than 6 months prior to entry will be required to have a negative or low probability cardiac stress test for cardiac ischemia.
- 3.1.10 CNS: No history of cerebrovascular accident or transient ischemic attacks.
- 3.1.11 The effects of entinostat on the developing human fetus at the recommended therapeutic dose are unknown. For this reason women of child-bearing potential must agree to use adequate contraception (hormonal or barrier method of birth control; abstinence) prior to study entry and for the duration of study participation. Should a woman become pregnant or suspect she is pregnant while participating in this study, she should inform her treating physician immediately. Men with female partners of child bearing potential must also agree to use adequate contraception.

3.1.12 Ability to understand and the willingness to sign a written informed consent document.

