### **Response Evaluation Criteria in Solid Tumors (RECIST V.1.0) Quick Reference**

Only patients with measurable disease at baseline should be included in protocols where objective tumor response is the primary endpoint.

**Measurable disease** - the presence of at least one measurable lesion. If the measurable disease is restricted to a solitary lesion, its neoplastic nature should be confirmed by cytology/histology.

**Measurable lesions** - lesions that can be accurately measured in at least one dimension with longest diameter  $\geq 20$  mm using conventional techniques or  $\geq 10$  mm with spiral CT scan.

**Non-measurable lesions** - all other lesions, including small lesions (longest diameter  $< 20$  mm with conventional techniques or  $< 10$  mm with spiral CT scan), i.e., bone lesions, leptomeningeal disease, ascites, pleural/pericardial effusion, inflammatory breast disease, lymphangitis cutis/pulmonis, cystic lesions, and also abdominal masses that are not confirmed and followed by imaging techniques; and.

- All measurements should be taken and recorded in metric notation, using a ruler or calipers. All baseline evaluations should be performed as closely as possible to the beginning of treatment and never more than 4 weeks before the beginning of the treatment.
- The same method of assessment and the same technique should be used to characterize each identified and reported lesion at baseline and during follow-up.
- Clinical lesions will only be considered measurable when they are superficial (e.g., skin nodules and palpable lymph nodes). For the case of skin lesions, documentation by color photography, including a ruler to estimate the size of the lesion, is recommended.

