### **Baseline documentation of “Target” and “Non-Target” lesions**

- All measurable lesions up to a maximum of five lesions per organ and 10 lesions in total, representative of all involved organs should be identified as *target lesions* and recorded and measured at baseline.
- Target lesions should be selected on the basis of their size (lesions with the longest diameter) and their suitability for accurate repeated measurements (either by imaging techniques or clinically).
- A sum of the longest diameter (LD) for *all target lesions* will be calculated and reported as the baseline sum LD. The baseline sum LD will be used as reference by which to characterize the objective tumor.
- All other lesions (or sites of disease) should be identified as *non-target lesions* and should also be recorded at baseline. Measurements of these lesions are not required, but the presence or absence of each should be noted throughout follow-up.

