## **9.2 Response Criteria**

### **9.2.1 Evaluation of target lesions**

- \* Complete Response (CR): Disappearance of all target lesions
- \* Partial Response (PR): At least a 30% decrease in the sum of the LD of target lesions, taking as reference the baseline sum LD

- \* Progressive Disease (PD): At least a 20% increase in the sum of the LD of target lesions, taking as reference the smallest sum LD recorded since the treatment started or the appearance of one or more new lesions
- \* Stable Disease (SD): Neither sufficient shrinkage to qualify for PR nor sufficient increase to qualify for PD, taking as reference the smallest sum LD since the treatment started

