### 9.2.2 Evaluation of non-target lesions

- \* Complete Response (CR): Disappearance of all non-target lesions and normalization of tumor marker level
- \* Incomplete Response/ Stable Disease (SD): Persistence of one or more non-target lesion(s) or/and maintenance of tumor marker level above the normal limits
- \* Progressive Disease (PD): Appearance of one or more new lesions and/or unequivocal progression of existing non-target lesions (1)

(1) Although a clear progression of “non-target” lesions only is exceptional, in such circumstances, the opinion of the treating physician should prevail and the progression status should be confirmed later on by the review panel (or study chair).

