### 11.3 Phase II

#### Primary Objective:

Once a recommended dose has been determined in the Phase I portion of the study, the cohort will be expanded so that 36 new patients will be treated at this dose level. The primary objective of this phase is to evaluate the safety and efficacy of the combination of entinostat and IL-2. The primary endpoint is overall response rate (complete plus partial). Enrollment is expected to be

between 1 and 2 patients per month. The combination treatment will be considered unsuccessful if the response rate is 20% or less, and it will be considered active enough to pursue further if the response rate was 40% or greater. To test this hypothesis, the fixed sample size for a single-stage study with a type I error of 10% and a type II error of 10%, based on an exact binomial test, is 36. If 11 or more of the patients have a response, the hypothesis that the response rate is  $\leq 20\%$  is rejected with a target error rate of 0.10. This design has type I and type II errors of 0.09 and 0.09, respectively.

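### Phase II admits patients without measurable disease although tumor response is the primary endpoint; if they enrol, the stated type II error of 0.09 is not assured

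*Combined protocol and SAP*

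**What the plan says.** **Eligibility.** Criterion 3.1.3 reads "Patients must have measurable or evaluable disease". Criterion 3.1.2 permits prior palliative radiation "provided there is at least one measurable and/or evaluable lesion(s) that has not been irradiated". The documents do not define evaluable disease.

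**Response criteria.** The RECIST 1.0 quick reference in Section 9 states: "Only patients with measurable disease at baseline should be included in protocols where objective tumor response is the primary endpoint". Its non-measurable lesions include bone lesions and those under 10 mm on spiral CT. Target lesions are drawn from measurable ones (9.1: "All measurable lesions up to a maximum of five lesions per organ and 10 lesions in total"). Partial response is "At least a 30% decrease in the sum of the LD of target lesions" (9.2.1). Complete response of non-target disease is "Disappearance of all non-target lesions and normalization of tumor marker level" (9.2.2). The overall-response table in 9.2.3 has no row for a patient without target lesions.

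**Design.** Section 11.3 makes complete plus partial response the primary endpoint. It treats 20% as unsuccessful and 40% as active, enrols 36 patients, and rejects the 20% hypothesis at 11 or more responses: "This design has type I and type II errors of 0.09 and 0.09, respectively".

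**Denominator.** Section 9.2.7 puts all eligible patients in the main response analysis. Section 11.7.2 bases conclusions on all eligible patients who start entinostat, and 11.7.3.1 includes everyone who starts protocol treatment. Section 11.7.2 also replaces patients found ineligible or *not evaluable*, without defining the latter.

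**The concern.** The eligibility list and the response section give different answers on who may enter a response-endpoint trial. A patient admitted on evaluable disease alone counts among the 36 but can count as a responder only through disappearance of all non-target disease, and the plan does not say whether that is an overall complete response. The sample-size text makes no allowance for such patients.

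What is at stake is a false negative: an active combination could be set aside more often than the 10% planned, in a single-stage trial with one decision rule. The scoring gap itself is narrow. Stable disease, progression and unknown status are all non-responses, so site-to-site differences in scoring can alter the primary endpoint only for a non-target-only complete response.

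**Working it through.** **Inputs.** From 11.3: n = 36, reject at 11 or more responses, null rate 0.20, alternative 0.40, target errors 10% and 10%. From 2.2: 22 responders on high-dose aldesleukin, 8 of them complete. Assumed, because the documents do not give them:
- k, the number of evaluable-only patients among the 36;
- c, the chance that such a patient has a counted complete response;
- whether 40% is the rate in measurable patients or in everyone enrolled;
- that evaluable-only means non-measurable by RECIST.

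**1. The plan's own figures.** With X ~ Binomial(36, p):
- P(X ≥ 11 | p = 0.20) = 0.0889;
- P(X ≥ 11 | p = 0.40) = 0.9096, so type II error is 1 − 0.9096 = 0.0904.

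Both round to the stated 0.09. The margin below the 10% target is under one percentage point.

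**2. Mixed cohort, with 40% as the rate in measurable patients.** Responses are X + Y, where X ~ Binomial(36 − k, 0.40) and Y ~ Binomial(k, c). Power = P(X + Y ≥ 11), by exact convolution. The illustrative c of 14.5% is 0.40 × 8/22, the complete-response share in 2.2 applied to a 40% rate. It is not a bound and is not shown to apply to non-measurable lesions.

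| k | Power, c = 0 | Power, c = 14.5% | Power, c = 30% | Type II error, c = 0 to 14.5% |
|---|---|---|---|---|
| 0 | 0.910 | 0.910 | 0.910 | 0.090 |
| 1 | 0.888 | 0.896 | 0.904 | 0.112 to 0.104 |
| 2 | 0.862 | 0.880 | 0.898 | 0.138 to 0.120 |
| 4 | 0.795 | 0.843 | 0.886 | 0.205 to 0.157 |
| 6 | 0.709 | 0.799 | 0.873 | 0.291 to 0.201 |

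**3. Break-even.** Solving P(X + Y ≥ 11) = 0.90 for c gives 22.4% (k = 1), 31.4% (k = 2), 35.7% (k = 4) and 37.2% (k = 6). Type II error exceeds 10% only when c is below these values. For context, complete response on high-dose aldesleukin alone in 2.2 was 8/95 = 8.4%.

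**4. Type I error.** With 0.20 in measurable patients and c from 0 to 7.3% (0.20 × 8/22), type I error is 0.075–0.080 at k = 1 and 0.041–0.056 at k = 4, against 0.0889 at k = 0. At c = 20% it returns to 0.0889.

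**5. The other reading: 40% in everyone enrolled.** The measurable-patient rate must then be higher. With c = 0 it is 0.40 × 36/(36 − k): 0.411 at k = 1 and 0.480 at k = 6. If c is 8/22 of the measurable-patient rate, that rate is 0.40 × 36/(36 − k + 8k/22): 0.407 and 0.447. Power is 0.910–0.924 for k = 1 to 6, so nothing is lost.

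**The case against.** The strongest objection is that 11.3 applies one response rate to 36 patients without limiting it to measurable disease, and the denominator rules also cover everyone treated. Read that way, 40% is the whole-cohort rate and step 5 shows the stated power holds. This stands as a condition: the power loss is real only on the other reading, and the documents do not settle which is meant.

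Second, the Section 9 sentence is quoted guidance worded as *should*, while Section 3 is the operative list. That is fair as to force, but the protocol adopts this guidance as its response criteria and the trial meets the stated condition.

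Third, *evaluable* is undefined, so equating it with non-measurable is an inference. Offering it as an alternative to measurable, however, has meaning only if it goes beyond measurable.

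Fourth, the replacement clause might remove these patients. It does not clearly do so: a patient admitted because the disease is evaluable is not obviously *not evaluable*, and 11.7.3.1 keeps everyone treated.

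Fifth, with no target lesions, the first row of the 9.2.3 table could be taken as met by default. That is one possible scoring, but the plan does not state it.

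Finally, k is unknown and could be zero, and the error is in the conservative direction. Both are true and limit the weight of the point.

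**Conclusion.** The concern holds. The conflict between 3.1.2/3.1.3 and Section 9, and the missing scoring rule, are firm and do not depend on k. The loss of power is conditional on evaluable-only patients enrolling, on 40% being the rate in measurable patients, and on c being below the break-even values. Under those conditions, and for c between 0 and 14.5%, a single such patient takes type II error to 0.104–0.112, past the 10% target, and four take it to 0.157–0.205. If none enrol, or if 40% describes the whole cohort, the stated 0.09 stands. There is no added false-positive risk.

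**What to change.** For Phase II, require at least one RECIST 1.0 measurable, non-irradiated lesion in 3.1.3 and in the radiation clause of 3.1.2. Phase I wording need not change: its objective is safety, and 4.1 reports that its recommended dose has been determined.

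The documents do not give accrual status. If evaluable-only patients are already enrolled:
- keep 11 of 36 treated patients as the primary rule;
- state in 9.2.3 how a patient without target lesions is scored, in particular whether non-target complete response counts as overall complete response;
- define *not evaluable* in 11.7.2 so that it agrees with 9.2.7 and 11.7.3.1;
- report k, with power at that k as a range over c and with the meaning of the 40% stated;
- give the measurable-disease response rate with its 95% confidence interval as supportive only, since 9.2.7 and 11.7.2 bar efficacy conclusions from subsets.

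**Cost.** The change is wording in four places, with no new procedures. At the planned 1 to 2 patients per month, refilling k places takes about k/2 to k months (0.5–1 month for k = 1, 2–4 months for k = 4). Excluded patients would no longer contribute to toxicity monitoring (11.4) or to the toxicity and PFS analyses (11.3), which would then describe measurable-disease patients only. A change partway through Phase II would also leave a cohort recruited under two eligibility rules, which the report should state.
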